#### **10.6. Subject Questionnaire**

Results from the subject questionnaire at baseline, and the 3 hour time point for Visit 2 (Stage 1 Day 8), Visit 4 (Stage 2 Day 1) and Visit 5 (Stage 2 Day 8) will be summarized by treatment group.

#### **10.7. Biomicroscopy and Ophthalmoscopy**

Results from biomicroscopic and ophthalmoscopic examinations at baseline, Visit 2 (Stage 1 Day 8) at the 12 hour post-dose time point, and Visit 5 (Stage 2 Day 8) at the 8 hour time point will be summarized by treatment group for the study eye and the fellow eye by treatment group.

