## 9. ASSESSMENT OF SAFETY

#### 9.1. Specification of Safety Parameters

The primary safety measures are subject-evaluated ocular tolerability and AEs. Other safety measures include biomicroscopy, ophthalmoscopy, BCDVA, IOP, subject questionnaire, and systemic safety (as measured by HR and BP). Urine pregnancy tests for females of childbearing potential will also be conducted.

The assessment of safety will be evaluated by:

- Ocular tolerability
- Biomicroscopy of the anterior segment including evaluation of lids, lashes, cornea, conjunctiva, iris, lens, and anterior chamber. Following topical fluorescein administration, the integrity of the cornea should be evaluated by fluorescein staining
- Ophthalmoscopy (direct or indirect) without dilation to evaluate the vitreous and posterior pole
- Best-corrected distance VA
- Intraocular pressure performed with a Tono-Pen or Goldmann Applanation tonometry
- Subject questionnaire
- Heart rate and BP (as per the site's normal equipment and procedures)
- Adverse events

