#### 9.3.1. Adverse Event Definitions

The following definitions of terms apply to this section:

*Adverse event*. An AE is any untoward medical occurrence associated with the use of a study medication in humans, whether or not it is considered drug related. An AE can therefore be any unfavorable and unintended sign (including abnormal laboratory findings), symptom, or disease temporally associated with the use of the study medication, whether or not related to the study medication. Study medication includes the investigational drug under evaluation and the comparator product or vehicle placebo that is given or administered during any phase of the study.

Medical conditions/diseases present before starting the investigational treatment are only considered AEs if they worsen after starting the investigational treatment. Abnormal test results constitute AEs only if they induce clinical signs or symptoms, are considered clinically significant, or require therapy.

The occurrence of AEs should be sought by open-ended questioning of the subject at each visit during the study. At each clinic assessment/visit, study personnel should ask the following question: "Have you had any problems since your last assessment/visit?" Adverse events also may be detected when they are volunteered by the subject during or between visits or through study assessments.

*Life-threatening adverse event or life-threatening suspected adverse reaction*. An AE or suspected adverse reaction is considered "life-threatening" if, in the view of either the Investigator or Ocuphire, its occurrence places the subject at immediate risk of death. It does not include an AE or suspected adverse reaction that, had it occurred in a more severe form, might have caused death.

*Serious adverse event or serious suspected adverse reaction*. An AE or suspected adverse reaction is considered "serious" if, in the view of either the Investigator or Ocuphire, it results in any of the following outcomes:

- Death
- Life-threatening AE
- Inpatient hospitalization or prolongation of existing hospitalization
- Persistent or significant incapacity or substantial disruption of the ability to conduct normal life functions
- Congenital anomaly/birth defect
- Other medically important serious event

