## **7.4. Planned Study Analyses**

### **7.4.1. Statistical Summaries: Descriptive and Inferential**

Categories for data presentation and analysis will consist of each treatment group: Nyxol and placebo for Stage 1, and Nyxol + LDP, Nyxol + LDP vehicle, Placebo + LDP, and Placebo + LDP vehicle for Stage 2.

All statistical tests will be two-sided and a difference resulting in a p-value of less than or equal to 0.05 will be considered statistically significant. The p-values for the analysis of secondary efficacy endpoints and safety endpoints will be considered descriptive, unless the endpoint is used for the hierarchical testing method. All p-values will be rounded to and displayed in four decimals. If a p-value less than 0.0001 occurs, it will be shown in tables as <0.0001.

Descriptive summaries of variables will be provided where appropriate. For continuous variables, the number of non-missing values (n), mean, standard deviation, median, minimum, and maximum will be tabulated by treatment group. For categorical variables, the counts and proportions of each value will be tabulated by treatment group. Expansion of descriptive table categories within each treatment may occur if such elaborations are thought to be useful.

All study-related data collected will be presented in listings. Study-related data not subject to analysis according to this plan will not appear in any tables or graphs but will be included in the data listings.

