#### **10.4. Vital Signs**

Descriptive statistics of observed values will be presented for vital sign data at baseline, Visit 2 (Stage 1 Day 8) at the 12 hour post-dose time point, and Visit 5 (Stage 2 Day 8) at the 8 hour time point by treatment group. Changes from baseline to each time point will be presented.

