#### **10.5. IOP**

Observed values and change from baseline in IOP at baseline, Visit 2 (Stage 1 Day 8) at the 12 hour post-dose time point, and Visit 5 (Stage 2 Day 8) at the 8 hour time point will be summarized for the study eye and the fellow eye by treatment group. Treatments will be compared using the same ANCOVA model proposed for the continuous secondary efficacy endpoints.

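### As visibly described, SAP 10.7 tabulates slit-lamp and fundus results visit by visit with no within-subject comparison to baseline, so mild findings that emerge on treatment are not separated from pre-existing ones

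*SAP*

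**What the plan says.** SAP 10.7 covers "Results from biomicroscopic and ophthalmoscopic examinations at baseline, Visit 2 (Stage 1 Day 8) at the 12 hour post-dose time point" and at the 8-hour time point of Visit 5. These results "will be summarized by treatment group for the study eye and the fellow eye by treatment group". The section names no change, shift, category of new findings, subject-level count or treatment comparison.

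SAP 7.4.1 supplies the default layout: "For categorical variables, the counts and proportions of each value will be tabulated by treatment group". Read with 10.7, this gives the distribution of results at each visit, separately for each eye.

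Neighbouring safety sections do use the subject's own baseline:
- Vital signs (SAP 10.4): "Changes from baseline to each time point will be presented".
- IOP (SAP 10.5): "Observed values and change from baseline in IOP at baseline" and at the same two later time points.
- Distance acuity (SAP 10.8): the percent of subjects losing at least 5 letters from baseline.

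Protocol 9.1 shows how much the examination covers: "Biomicroscopy of the anterior segment including evaluation of lids, lashes, cornea, conjunctiva, iris, lens, and anterior chamber", with the vitreous and posterior pole assessed by ophthalmoscopy. Protocol 10.3.6 describes no analysis of these examinations beyond by-subject listings.

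**The concern.** The safety question for an eye drop is what appears on treatment. Subjects are 40 to 64 years old. The exclusion criteria remove clinically significant ocular disease that might interfere, but minor lid, lens or conjunctival findings can still be present at entry. If they persist, they are counted again at Visit 2 and Visit 5. In a visit-by-visit table, a subject who loses a finding offsets one who gains it, and only the net figure shows. Because both eyes are treated and tabulated separately, no count of subjects with a new finding in either eye results.

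At stake is how easily a modest excess of mild findings would be seen. The randomized comparison at each visit remains valid.

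**Working it through.** **No figure to reproduce.** The documents state none for this point. The check is a reading of the text followed by an illustration.

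**Reading.** SAP 10.7 with 7.4.1 gives counts per visit and eye. Sections 10.4, 10.5 and 10.8 refer to baseline. Both examinations are scheduled at Visits 1, 2 and 5 (protocol Tables 1 and 2), so the paired data will exist.

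**Inputs from the documents.** About 80 subjects per arm in Stage 2 and about 160 per group in Stage 1 (SAP 5.1).

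**Assumptions, not in the documents.** A share b of subjects has the finding at baseline, equal across arms and persistent. Among those free of it, it appears in 5% on drug (r1) and 1% on placebo (r0). The range for b is 0 to 30%.

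**Formulas, per arm, with n = 80.**
- Visit prevalence: p = b + (1 − b)r.
- New findings as a share of all subjects: q = (1 − b)r.
- Both give the same between-arm difference, (1 − b)(r1 − r0).
- SE of the difference = √[(x1(1 − x1) + x0(1 − x0))/80], with x = p or x = q.

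**Example, b = 10%.** p1 = 0.10 + 0.90 × 0.05 = 0.145 and p0 = 0.10 + 0.90 × 0.01 = 0.109. SE = √[(0.1240 + 0.0971)/80] = 0.053. For new findings, q1 = 0.045 and q0 = 0.009, so SE = √[(0.0430 + 0.0089)/80] = 0.025. The ratio is 2.1.

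| b | Difference (points) | SE, visit prevalence (points) | SE, new findings (points) | Ratio |
|---|---|---|---|---|
| 0 | 4.0 | 2.7 | 2.7 | 1.0 |
| 5% | 3.8 | 4.2 | 2.6 | 1.6 |
| 10% | 3.6 | 5.3 | 2.5 | 2.1 |
| 20% | 3.2 | 6.6 | 2.4 | 2.7 |
| 30% | 2.8 | 7.4 | 2.3 | 3.3 |

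The ratios do not depend on n, so they apply to Stage 1 as well.

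**A larger assumed effect: 15% versus 5% onset.** Two-sided alpha is 0.05, and power = Φ[(d − 1.96·SE₀)/SE₁], where d is the difference, SE₀ the pooled and SE₁ the unpooled standard error. New findings are analysed in the n(1 − b) subjects at risk.

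| n per arm | b | Power, visit prevalence | Power, new findings |
|---|---|---|---|
| 80 | 0 | 0.56 | 0.56 |
| 80 | 10% | 0.30 | 0.52 |
| 80 | 30% | 0.15 | 0.42 |
| 160 | 10% | 0.54 | 0.81 |
| 160 | 30% | 0.25 | 0.71 |

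SAP 10.7 plans no test, so these powers only describe relative sensitivity.

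**The case against.** The case against has five parts.

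1. **The table list is redacted.** A reader might infer that the plan contains no shift table at all. The documents do not support that: the layouts belong to SAP 12.1, which is blacked out, and SAP 7.4.1 allows descriptive categories to be expanded. This stands, and the point is confined to the visible text of 10.7.

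2. **Important findings are already counted.** A reader might infer that emerging ocular findings go uncounted. They do not. Under protocol 9.3.1, pre-existing conditions "are only considered AEs if they worsen after starting the investigational treatment", and "Abnormal test results constitute AEs only if they induce clinical signs or symptoms, are considered clinically significant, or require therapy". SAP 10.1 then counts each subject once per term. This also stands. What remains is findings below that threshold. They appear in the visit tables and in by-subject listings, and listings allow case review but do not compare arms.

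3. **Conjunctival hyperemia.** It was the most frequent event in earlier Nyxol studies, so a reader might cite it as the signal that would be missed. Protocol 9.3.1 already prescribes adverse event terms for redness gone by 2 hours and for redness still present. The later examinations fall about 12 hours after Treatment 1 at Visit 2 and about 12 + 8 = 20 hours after it at Visit 5. Transient redness would be absent then under any table format. The example is largely covered.

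4. **Data type.** Vital signs and IOP are continuous, so change from baseline comes naturally; examination results are categorical. This has limited force, because SAP 10.8 treats a categorical outcome relative to baseline.

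5. **Assumed rates.** The exclusions limit baseline findings, and with none there is no loss. In the 5% versus 1% illustration, the difference is only 1.2 to 1.4 standard errors for new findings at b of 10% to 30%, against 0.4 to 0.7 for prevalence, so neither table would establish it. Both remarks are fair.

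**Conclusion.** The point holds as a small improvement to the plan, and the plan is not in error. The visible SAP 10.7 offers no within-subject comparison to baseline, unlike 10.4, 10.5 and 10.8, and so does not separate mild findings that emerge on treatment from those present at entry.

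Under the stated assumptions, visit prevalence has a standard error 2.1 to 3.3 times that of new findings when 10% to 30% of subjects have a persistent baseline finding, 1.6 times at 5%, and the same at zero. The documents give neither baseline prevalence nor onset rates, so the actual loss is unknown.

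A reader might also take this for a bias between arms. It is not one: baseline is tabulated at its own time point and the arms are randomized. Only sensitivity is reduced.

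**What to change.** First check whether the redacted planned tables already contain a shift or new-finding summary. If they do, say so in SAP 10.7. If not, add:

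- For each structure examined, a shift table from baseline to Visit 2 and from baseline to Visit 5.
- The number and percent of subjects with a new finding in either eye, meaning that the structure was normal or the finding absent in that eye at baseline. Count each subject once, among those examined at both visits.
- Worsened findings as well, but only where the eCRF grades them. Protocol 5.1 leaves the examinations to each site's standard practice and the documents show no grading scale, so this part may not be feasible.

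Present these by Stage 1 treatment at Visit 2 and by the four arms at Visit 5, in the Safety Population by treatment actually received. Keep the by-eye summaries as support. No test is needed.

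The cost is one paragraph in the SAP and two descriptive tables from examinations already scheduled. No new procedure is required.

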#### **10.8. Other Safety Measures**

The percent of subjects who lose  $\geq 5$  letters from Baseline in photopic BCDVA will be summarized within the summary of secondary efficacy endpoint Percentage of subjects with loss or improvement in photopic and mesopic BCDVA from baseline. Treatments will be compared using the same logistic regression model proposed for the secondary efficacy endpoints.

Urine pregnancy tests for females of childbearing potential will be presented in by-subject listings. Dry eye tests (tear break-up time and cornea fluorescein staining), performed only at baseline, will also be listed.

[REDACTED]	[REDACTED]				[REDACTED]	
[REDACTED]	[REDACTED]					[REDACTED]
[REDACTED]	[REDACTED]				[REDACTED]	
[REDACTED]	[REDACTED]					[REDACTED]
[REDACTED]	[REDACTED]				[REDACTED]	
[REDACTED]	[REDACTED]					[REDACTED]
[REDACTED]	[REDACTED]				[REDACTED]	
[REDACTED]	[REDACTED]					[REDACTED]

[REDACTED]	[REDACTED]	[REDACTED]	[REDACTED]	[REDACTED]	[REDACTED]	[REDACTED]
[REDACTED]	[REDACTED]					
[REDACTED]	[REDACTED]				[REDACTED]	
[REDACTED]	[REDACTED]					[REDACTED]
[REDACTED]	[REDACTED]				[REDACTED]	
[REDACTED]	[REDACTED]					[REDACTED]
[REDACTED]	[REDACTED]				[REDACTED]	
[REDACTED]	[REDACTED]					[REDACTED]
[REDACTED]	[REDACTED]				[REDACTED]	
[REDACTED]	[REDACTED]					[REDACTED]
[REDACTED]	[REDACTED]				[REDACTED]	
[REDACTED]	[REDACTED]					[REDACTED]
[REDACTED]	[REDACTED]				[REDACTED]	
[REDACTED]	[REDACTED]					[REDACTED]

[REDACTED]	[REDACTED]	[REDACTED]	[REDACTED]	[REDACTED]	[REDACTED]	[REDACTED]
	[REDACTED]					
[REDACTED]	[REDACTED]				[REDACTED]	
[REDACTED]	[REDACTED]					[REDACTED]
[REDACTED]	[REDACTED]				[REDACTED]	
[REDACTED]	[REDACTED]					[REDACTED]
[REDACTED]	[REDACTED]				[REDACTED]	
[REDACTED]	[REDACTED]					[REDACTED]
[REDACTED]	[REDACTED]				[REDACTED]	

[REDACTED]	[REDACTED]	[REDACTED]	[REDACTED]	[REDACTED]	[REDACTED]	[REDACTED]
[REDACTED]	[REDACTED]					[REDACTED]
[REDACTED]	[REDACTED]			[REDACTED]		
[REDACTED]	[REDACTED]			[REDACTED]		
[REDACTED]	[REDACTED]		[REDACTED]			
[REDACTED]	[REDACTED]		[REDACTED]			
[REDACTED]	[REDACTED]		[REDACTED]			
[REDACTED]	[REDACTED]		[REDACTED]			
[REDACTED]	[REDACTED]		[REDACTED]			
[REDACTED]	[REDACTED]		[REDACTED]			
[REDACTED]	[REDACTED]		[REDACTED]			
[REDACTED]	[REDACTED]		[REDACTED]			
[REDACTED]	[REDACTED]		[REDACTED]			
[REDACTED]	[REDACTED]		[REDACTED]			
[REDACTED]	[REDACTED]		[REDACTED]			

[REDACTED]

[REDACTED]
